**APPENDIX B**

[figure not shown]
**DEPARTMENT OF RADIATION AND CELLULAR ONCOLOGY**  
DIVISION OF THE BIOLOGICAL SCIENCES AND  
THE PRITZKER SCHOOL OF MEDICINE

This questionnaire is a supplement to the standard of care questionnaire used for all patients treated for prostate cancer in our department. These questions are aimed at further describing your general state of well being, under the study IRB:\_\_\_\_: “A Phase II study of oral hormonal therapy and radiation therapy for non-metastatic, intermediate or high risk prostate cancer in men with advanced age or medical comorbidity.”

**Please note that there are 2 sides on each page.**

To help people say how good or bad a health state is, we have drawn a scale (rather like a thermometer) on which the best state you can imagine is marked by 100 and the worst state you can imagin is marked by 0.

We would like you to indicate in this scale how good or bad is your own health today, in your opinion. Please do this by drawing an “X” on the line at whichever point on the scale indicates how good or bad your current health is.

Physician use only:							
Baseline	Pre-ADT	Pre-RT	2 mos post-RT	6 mos post-RT	12 mos post-RT	18 mos post-RT	24 mos post-RT
STUDY VISIT:							
(circle month)	0	2	3-4	10	16	22	28

The following questions are about your **energy and overall well being**.

2. **Over the last 4 weeks**, how often have you experienced hot flashes?

- More than once a day.....1
- About once a day.....2
- More than once a week.....3 (Circle one number)
- About once a week.....4
- Rarely or never.....5

3. How often have you had breast tenderness **during the last 4 weeks**?

- More than once a day.....1
- About once a day.....2
- More than once a week.....3 (Circle one number)
- About once a week.....4
- Rarely or never.....5

4. **During the last 4 weeks**, how often have you felt depressed?

- More than once a day.....1
- About once a day.....2
- More than once a week.....3 (Circle one number)
- About once a week.....4
- Rarely or never.....5

5. **During the last 4 weeks**, how often have you felt a lack of energy?

- More than once a day.....1
- About once a day.....2
- More than once a week.....3 (Circle one number)
- About once a week.....4
- Rarely or never.....5

6. How much change in your weight have you experienced **during the last 4 weeks**, if any?

- Gained 10 pounds or more.....1
- Gained less than 10 pounds.....2
- No change in weight.....3 (Circle one number)
- Lost less than 10 pounds.....4
- Lost 10 pounds or more.....5

7. How big a problem **during the last 4 weeks**, if any, has each of the following been for you?

	No Problem	Very Small Problem	Small Problem	Moderate Problem	Big Problem
a. Hot flashes.....	0	1	2	3	4
b. Breast tenderness/ enlargement.....	0	1	2	3	4
c. Feeling Depressed.....	0	1	2	3	4
d. Lack of energy.....	0	1	2	3	4
e. Change in body weight .....	0	1	2	3	4

8. Overall, how big a problem has hormonal therapy been for you **during the last 4 weeks**?

- No Problem.....1
  - Very small problem.....2
  - Small problem.....3
  - Moderate problem.....4
  - Big problem.....5
- (Circle one number)

9. Please respond to each by circling one number per row.

	Excellent	Very Good	Good	Fair	Poor
a. In general, would you say your health is:.....	1	2	3	4	5
b. In general, would you say your quality of life is: .....	1	2	3	4	5
c. In general, how would you rate your physical health? :.....	1	2	3	4	5
d. In general, how would you rate your mental health, including your mood and your ability to think? .....	1	2	3	4	5

	Excellent	Very Good	Good	Fair	Poor
e. In general, how would you rate your satisfaction with your social activities and relationships? .....	1	2	3	4	5

f. In general, please rate how well you carry out your usual social activities and roles (This includes activities at home, at work and in your community, and responsibilities as a parent, child, spouse, employee, friend, etc.) .....	1	2	3	4	5
---	---	---	---	---	---

10. To what extent are you able to carry out your everyday physical activities such as walking, climbing stairs, carrying groceries, or moving a chair?

Never.....	1	
Rarely.....	2	
Sometimes.....	3	(Circle one number)
Often.....	4	
Always .....	5	

11. In the past 7 days, how often have you been bothered by emotional problems such as feeling anxious, depressed or irritable?

Not at All.....	1	
A Little.....	2	
Moderately.....	3	(Circle one number)
Mostly.....	4	
Completely .....	5	

12. In the past 7 days, how would you rate your fatigue on average?

None.....	1	
Mild.....	2	
Moderate.....	3	(Circle one number)
Severe.....	4	
Very Severe .....	5	

Signature \_\_\_\_\_

Date \_\_\_ / \_\_\_ / \_\_\_\_\_

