### **4.2. Measuring Health-Related Quality of Life and Toxicity**

Patient-reported outcome measures will include a modified version of the Expanded Prostate Cancer Index Composite (EPIC-26) which has been validated as an alternative to the complete questionnaire (EPIC-50).[33] The questionnaire will include all EPIC-26 items as well as additional items in the hormonal/vitality domain drawn from the full length EPIC-50. General

health-related quality of life, including fatigue, will be assessed with the PROMIS v1.0 Global short form and the EQ-5D visual scale for quality of life. All items will be consolidated into 2 questionnaires. The first questionnaire is the standard questionnaire administered to all patients with prostate cancer in the department of radiation oncology (see Appendix A). A supplemental four page questionnaire will be administered to all patients on trial and to all consenting control patients at baseline (see Appendix B). Both questionnaires will again be administered at 1-2 months after initiation of hormonal treatment (before RT), at 3-4 months (during RT), and at 6 months after initiation of study therapy. Questionnaires will be completed in writing by the patient. Questionnaires at 12, 18, and 24 months after completion of radiation therapy will not be required, although any collected data over this time frame will be recorded and available for analysis.

The evaluation period of acute radiation-related toxicity will be defined by the period from the start of radiation to three months following the completion of radiation. Toxicity will be graded according to Radiation Therapy Oncology Group (RTOG) acute toxicity scale (see Appendix D). Toxicity will be recorded on a weekly basis during radiation treatment and at the first follow up visit. Chronic toxicities will also be graded according to the RTOG toxicity scale and will be recorded at each point of clinical contact beyond the third month after completion of radiation.

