#### **4.3. Experimental Controls**

Patients who meet eligibility criteria of the study but who do not enroll on the trial who receive standard ADT with radiation will be approached for participation in the parallel data collection study. These patients will serve as the control group with which to compare HRQOL outcomes of patients treated on trial. Patients consenting to enrollment on the parallel data collection study will receive standard of care treatment, follow-up, imaging, and laboratory studies not subject to the plan described in this protocol. Health information may be recorded from the electronic medical record. Patients on the data collection study will be asked to complete the same supplemental four-page questionnaire (see Appendix B) as those on trial at baseline, 1-2 months after initiation of standard ADT (before RT), and at 6 months. Completion of the supplemental questionnaire will not be required at 12, 18, and 24 months after initiation of radiation, however any collected data over this time frame will be recorded and available for analysis. In addition, all controls will complete the six-page questionnaire which is standard practice for all patients treated in the department of radiation oncology according to usual practice.

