### 7. STUDY CALENDAR

Baseline evaluations (including performance status, history and physical, scans) are to be conducted within 60 days prior to the start of protocol therapy.

	Baseline	Month 2 (pre-RT)	Month 3-4 (during RT)	Month 6 (2 mos post- RT)	Month 10 (6 mos post-RT)	Month 16 (12 mos post-RT)	Month 22 (18 mos post-RT)	Month 28 (24 mos p RT)
Inclusion/ exclusion	X							
Informed Consent	X							
Path confirms cancer	X							
History and Physical	X	X	X**	X	X	X	X	X
Vital Signs, weight	X		X**	X	X	X	X	X
Zubrod Performance status and Charlson index	X							
Document Current Medicines	X	X	X**	X	X	X	X	X
CT Ab/Pelvis OR MRI*	X							
Bone Scan *	X							
Tumor tissue collection	X	X						
CBC with differential and CMP	X	X	X#	X		X		X
Toxicity Assessment			X**	X	X	X	X	X
Patient Outcome Questionnaire	X	X		X	X	X≠	X≠	X≠
PSA	X	X		X	X	X	X	X

Total, serum Testosterone	X	X				X		X
---------------------------	---	---	--	--	--	---	--	---

^ This evaluation will occur at the planning stage before radiation therapy has begun (e.g. fiducial marker placement or simulation)

\* See Section 3 for requirements/exceptions \*\* Weekly during radiation treatment

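### Appendix B items 10 and 11 carry answer scales that do not fit their questions; the two sets appear to have been exchanged

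*Combined protocol and SAP*

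**What the plan says.** Section 4.2 states that general quality of life, including fatigue, "will be assessed with the PROMIS v1.0 Global short form and the EQ-5D visual scale". Patients complete the questionnaires themselves in writing. The general-health items are printed in the Appendix B supplement as 9a to 9f, 10, 11 and 12.

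- Item 10 asks "To what extent are you able to carry out your everyday physical activities such as walking, climbing stairs, carrying groceries, or moving a chair". Its printed answers are Never, Rarely, Sometimes, Often, Always (1 to 5).
- Item 11 asks "In the past 7 days, how often have you been bothered by emotional problems such as feeling anxious, depressed or irritable". Its printed answers are Not at All, A Little, Moderately, Mostly, Completely (1 to 5).

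Section 4.3 gives control patients the same "supplemental four-page questionnaire (see Appendix B) as those on trial at baseline" and at later visits, so both cohorts answer the same wording. Section 9.1 makes global quality of life one of the domains of the 6-month primary endpoint and of the composite score, but lists no items for either. Section 9.2 defines success on the hormonal/vitality domain only.

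**The concern.** A patient asked how often something happened has to reply with a degree such as Mostly or Completely. A patient asked to what extent he can do something has to reply with a frequency. Each patient must then decide what was meant, and patients may decide differently. The answers are no longer standardised responses to a defined question.

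What is at stake depends on scoring that section 9.1 leaves open. If items 10 and 11 enter the global score, the validity of part of a primary-endpoint domain is weakened, and so is part of the composite. Applying a standard scoring rule for the named short form to these two items also becomes questionable. If they stay outside the score, only their item-level results are affected. The point also bears on the study's purpose: section 9.1 says the data are to help define the expected range of quality-of-life change for a later randomised comparison, so an uncorrected form could be carried forward.

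**Working it through.** No sample size, power or alpha figure depends on this point, and the plan states no figure to reproduce. The check is a comparison of wording, followed by counts of exposure.

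**1. Question against answer set (Appendix B)**

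| Item | Question asks for | Printed answers give | Fit |
|---|---|---|---|
| 10 | extent | frequency (Never to Always) | no |
| 11 | frequency | degree (Not at All to Completely) | no |
| 12 | level of fatigue | severity (None to Very Severe) | yes |

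Items 10 and 11 are adjacent, both sets are complete with five options coded 1 to 5, and exchanging them makes both items coherent.

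**2. Other frequency questions.** Appendix B has five items that ask how often: 2, 3, 4, 5 and 11. Items 2 to 5 all offer frequency answers, including item 4, which asks "how often have you felt depressed". Appendix A has fourteen more: items 1, 6a to 6f, 7, 8, 9, 17, 20b, 20c and 20e (1 + 6 + 1 + 1 + 1 + 1 + 3 = 14), all with frequency answers. So 4 + 14 = 18 of 19 are coherent, and item 11 is the sole exception.

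**3. Could text extraction have swapped the blocks?** This is unlikely. Each answer block follows its own question with its own instruction to circle one number, and item 12 directly below is intact.

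**4. Direction of the codes.** Item 10 runs from least to most able under either set. Item 11 runs from least to most bothered under either set. The exchange reverses no score.

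**5. Share of the general-health items.** 9a to 9f (6) + 10 + 11 + 12 = 9, so 2/9 = 22%. If item 12 serves only the fatigue domain, 2/8 = 25%.

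**6. Exposed forms through month 6** (40 trial and 30 control patients, no dropout). The visit schedule is not uniform. Section 4.2 repeats both questionnaires before RT and then "at 3-4 months (during RT), and at 6 months after initiation of study therapy", which makes four visits with baseline. The "Patient Outcome Questionnaire" row of the section 7 calendar shows no mark at month 3-4, which leaves three. Section 4.3 gives controls three.

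| Reading | Forms | Answers to items 10 and 11 |
|---|---|---|
| Calendar for trial, 4.3 for controls | 3×40 + 3×30 = 210 | 420 |
| 4.2 for trial, 4.3 for controls | 4×40 + 3×30 = 250 | 500 |
| 4.2 read as four visits for both | 4×40 + 4×30 = 280 | 560 |

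On every reading, baseline and month 6 give 70 × 2 = 140 forms, or 280 answers. These are the forms that bear on the 6-month endpoint.

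**7. Mixed versions if the form changes mid-accrual.** Section 9.2 plans 2 trial patients per month per site and 1 to 2 controls per month. With one site, that is 3 to 4 per month. Patients with one version at baseline and another at month 6: 6 × 3 = 18 to 6 × 4 = 24. Section 7 allows the month 6 visit at month 5 or 7, which widens this to 5 × 3 = 15 to 7 × 4 = 28.

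**The case against.** The strongest reply is that little hangs on this. The only defined success rule uses the hormonal/vitality score; both cohorts answer the same form; both printed scales are ordered in the right direction and can be answered; and related content is covered elsewhere (items 4, 7c and 9d for mood; 9a, 9b and the visual scale for global quality of life). That stands as a limit on severity. It does not restore the two items: equal exposure in both cohorts does not make an ill-formed question valid.

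A second reply is that the exchange is only inferred. Items 2 to 5 use a different frequency scale, running from more than once a day to rarely or never. They show that item 11 is out of line, but not which frequency set it should carry, and they say nothing about item 10. This is fair. The exchange itself rests on adjacency and mutual fit. The mismatch, however, is plain on the page and needs no inference. The documents do not reproduce the named short form or its scoring, so the source page and that form should be checked before reprinting.

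Third, the remedy has limits. Keeping the direction of the codes does not make Often equivalent to Mostly across versions. Dropping item 10 also removes the form's only question on everyday physical activities, so a score without it differs in content as well as in version. Both points stand. The with/without comparison is a sensitivity check, not a full correction.

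Finally, the largest form count (280) sits poorly with section 4.3, which gives controls three visits. The 140 forms at baseline and month 6 hold regardless.

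**Conclusion.** The concern holds. Items 10 and 11 of Appendix B are mismatched with their answer sets as printed, and an exchange of the two sets is the most natural explanation. The defect touches 2 of 9 general-health items and, at full accrual without dropout, 280 answers at baseline and month 6. These are counts of exposure, not effect sizes; the documents do not allow the measurement error to be quantified.

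The effect on the primary endpoint is conditional on whether the items enter the global and composite scores. No between-group bias, no score reversal, and no effect on the hormonal/vitality criterion or n=40 follows. The conclusion assumes that the extracted text reflects the printed page. It should be corrected because patients complete the form themselves and the correction is cheap, but it does not threaten the design.

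**What to change.** 1. Check items 10 and 11 on the source page and against the named short form, then exchange their answer sets.
2. Record which form version each patient completed at each visit.
3. State in section 9.1 whether items 10 and 11 enter the global and composite scores.
4. If forms with the printed wording have been used, report those scores with and without the two items in both cohorts.

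The cost is one corrected form with its approval, one version variable, one sentence in 9.1 and, where needed, a second report of two scores. Stored answers keep their direction and need no recoding. If the form is changed before the first patient, no one has mixed versions. If it is changed mid-accrual, about 18 to 24 of the 70 patients would have different versions at baseline and month 6 (15 to 28 with the visit window). This assumes one site, planned accrual in both cohorts and no dropout. A change three months into accrual would affect fewer, about 3 × 3 = 9 to 3 × 4 = 12. The version record identifies these patients.

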## APPENDIX C:

### Charlson Comorbidity Index:

Comorbidity should be recorded according to the defined criteria in the original publication of Charlson, et al.

**Myocardial infarct:** Includes patients with one or more definite or probable myocardial infarctions; these patients have been hospitalized and had electrocardiographic and/or enzyme changes. Patients with electrocardiographic changes alone were not designated as having had an infarction.

**Congestive heart failure:** Includes patients who have had exertional or paroxysmal nocturnal dyspnea and who have responded symptomatically (or on physical examination) to digitalis, diuretics, or afterload reducing agents. It does not include patients who are on medication but have had no symptomatic response and no evidence of improvement of physical signs.

**Peripheral vascular disease:** Includes patients with intermittent claudication or those who had a bypass for arterial insufficiency and those with gangrene or acute arterial insufficiency and those with an untreated thoracic or abdominal aneurysm. (6 cm or more).

**Hypertension:** Includes patients with diastolic pressure over 100 mmHg and those with controlled hypertension on medications.

**Chronic Pulmonary Disease:** Moderate pulmonary disease is dyspneic with slight activity, with or without treatment and those who are dyspneic with moderate activity despite treatment. Severe pulmonary disease includes patients who are dyspneic at rest, despite treatment, those who require constant oxygen, those with CO2 retention and those with a baseline PO2 <50 mmHg.

**Cerebrovascular disease:** Includes patients with a history of a cerebrovascular accident with minor or no residua and transient ischemic attacks

**Dementia:** Includes patients with chronic cognitive deficit.

**Renal Disease:** Moderate renal disease includes patients with serum creatinine of >3 mg/dl. Severe renal disease includes patients on dialysis those who had a transplant and those with uremia

**Liver disease:** Severe liver disease consists of patients with cirrhosis, portal hypertension, and a history of variceal bleeding. Moderate liver disease consists of cirrhosis with portal hypertension and without bleeding.

**Lymphoma** includes patients with Hodgkins, lymphosarcoma, Waldenstroms macroglobulinemia, myeloma, and other lymphomas.

**Leukemia** includes patients with acute and chronic myelogenous leukemia, acute and chronic lymphocytic leukemia, and polycythemia vera.

**Tumor** consists of patients with solid tumors without documented metastases but initially treated in the last 5 years including breast, colon, lung, and other tumors. Does not include the diagnosis under study (prostate cancer).

Table 3. Weighted index of comorbidity

Assigned weights for diseases	Conditions
1	Myocardial infarct Congestive heart failure Peripheral vascular disease Cerebrovascular disease Dementia Chronic pulmonary disease Connective tissue disease Ulcer disease Mild liver disease Diabetes
2	Hemiplegia Moderate or severe renal disease Diabetes with end organ damage Any tumor Leukemia Lymphoma
3	Moderate or severe liver disease
6	Metastatic solid tumor AIDS

Assigned weights for each condition that a patient has. The total equals the score. Example: chronic pulmonary (1) and lymphoma (2) = total score (3).

Charlson, M.E., et al., *A new method of classifying prognostic comorbidity in longitudinal studies: development and validation*. J Chronic Dis, 1987. **40**(5): p. 373-83.

Hall, W.H., et al., *An electronic application for rapidly calculating Charlson comorbidity score*. BMC Cancer, 2004. **4**: p. 94.

**APPENDIX D:**

**RTOG Toxicity Scale**

GU Toxicity

	Grade 1	Grade 2	Grade 3	Grade 4
Acute RTOG	Frequency of urination or nocturia twice pretreatment habit/ dysuria, urgency not requiring medication	Frequency of urination or nocturia which is less frequent than every hour. Dysuria, urgency, bladder spasm requiring local anesthetic (e.g., Pyridium)	Frequency with urgency and nocturia hourly or more frequently/ dysuria, pelvis pain or bladder spasm requiring regular, frequent narcotic/gross hematuria with/ without clot passage	Hematuria requiring transfusion/ acute bladder obstruction not secondary to clot passage, ulceration or necrosis
Late RTOG BLADDER	Slight epithelial atrophy Minor telangiectasia (microscopic hematuria)	Moderate frequency Generalized telangiectasia Intermittent macroscopic hematuria	Severe frequency and dysuria Severe generalized telangiectasia (often with petechiae) Frequent hematuria Reduction in bladder capacity (<150 cc)	Necrosis/ Contracted bladder (capacity <100 cc) Severe hemorrhagic cystitis

GI Toxicity

	Grade 1	Grade 2	Grade 3	Grade 4
Acute RTOG	Increased frequency or change in quality of bowel habits not requiring medication/ rectal discomfort not requiring analgesics	Diarrhea requiring parasympatholytic drugs (e.g. Lomotil)/ mucous discharge not necessitating sanitary pads/ rectal or abdominal pain requiring analgesics	Diarrhea requiring parenteral support/ severe mucous or blood discharge necessitating sanitary pads/abdominal distention (flat plate radiograph demonstrates distended bowel loops)	Acute or subacute obstruction/fistula or perforation; GI bleeding requiring transfusion; abdominal pain or tenesmus requiring tube decompression or bowel diversion
Late RTOG SMALL/LARGE INTESTINE	Mild diarrhea Mild cramping Bowel movement 5 times daily Slight rectal discharge or bleeding	Moderate diarrhea and colic Bowel movement >5 times daily Excessive rectal mucus or intermittent bleeding	Obstruction or bleeding requiring surgery	Necrosis/ Perforation Fistula
